Appendix A: Case report forms

Case report forms will be provided under separate cover upon request.

Appendix B: Informed consent template

Informed Consent form templates will be provided under separate cover.

Appendix C: Participating investigators and institutions

A complete list of participating investigators and institutions where study activities are conducted will be maintained by the Sponsor and distributed under separate cover upon request.

Appendix D: Study Sponsor Contact Information

The study sponsor contact list will be provided in the site's study documents binder/investigator site file. Sponsor will maintain this list and send update if necessary.

Appendix E: Investigator Reporting Requirements

Investigator Reporting Requirements for India		
Events to Report	Reporting Requirement and Timeframe	Submit to
Cardiovascular Related SAE/SADE/USADE		
Investigator submit to:		
All SAE, SADE, USADE	
Investigator shall report all SAEs, SADEs and USADEs to the Ethics Committee, monitor and Sponsor promptly of their occurrence. (Indian GCP section 3.3.4.3)
 
For reported deaths the investigator shall supply any additional information (e.g., autopsy report and terminal medical reports.) (Indian GCP section 3.3.4.5)
 
It is recommended for investigator to report all SAEs, SADEs and USADEs to the sponsor within 24 hours.
 
It is recommended for investigator to report all SAEs, SADEs and USADEs to EC within 7 working days unless the stricter timeline is required by the EC.
	Medtronic Monitor EC
New information that may adversely affect safety of the subjects or the conduct of the study	Investigator shall promptly report new information that may adversely affect safety of the subject or the conduct of the study. (Indian GCP section 3.3.4.4)	EC Medtronic Monitor

Investigator Reporting Requirements for Korea		
Events to Report	Reporting Requirement and Timeframe	Submit to
Cardiovascular Related SAE/SADE/USADE		
Investigator submit to:		
All SAE	The investigator shall create and submit relevant document for all SAEs (excluding what classified in the protocol or the IB as ones not requiring immediate report) to the sponsor within the period provided in the protocol. (KGCP Article 7 item 11)	Medtronic
SADEs, USADEs causing death or life threatening	
Within 7 calendar days from the date when the investigator had relevant effects reported or informed. In this case, the investigator shall make a detailed report of the SADEs, USADEs causing death or life threatening within 8 calendar days from the initial report.
 
For Death, investigator shall submit additional information, such as
	IRB

	an autopsy report (only if an autopsy was performed) and a death certificate.	
Other SADEs, USADEs excluding death or life threatening	Within 15 calendar days from the date when the investigator had relevant effects reported or informed.	IRB

Investigator Reporting Requirements for Taiwan

Investigator Reporting Requirements for Taiwan		
Events to Report	Reporting Requirement and Timeframe	Submit to
Cardiovascular Related SAE		
Investigator submit to:		
SAE	
The investigator should report SAEs to the sponsor immediately. A detailed written report should be provided to the sponsor as soon as possible.
 
(Medical Device GCP Guidance (2016-01-01) Article 67)
 
It is recommended for investigator to report all SAEs to the sponsor within 48 hours.
	Medtronic
SAE	
Report within 7 calendar days of first acknowledged of death and life-threatening SAEs, SADEs and USADEs, make a report and submit to TFDA and ADR center, submit a copy to the sponsor.
 
If the information of the report mentioned in the preceding paragraph is not complete, it should be supplied within 15 calendar days.
 
If the information of the report mentioned in the preceding paragraph requires the sponsor to provide information relevant to the products, the sponsor should not refuse.
 
Note: The requirement is not applicable if MDT is not the product license holder.
 
(Procedure for Reporting Severe Adverse Reactions to Medicines (2004-8-31) Article 5)
 
It is recommended to report all non-fatal or non-life- threatening SADEs and USADEs following the same requirements mentioned above.
	TFDA

Acute myocardial infarction (MI) is a life-threatening condition that occurs when the blood flow to the heart muscle is abruptly cut off, causing tissue damage. Left ventricular dysfunction following an acute MI identifies patients at higher risk of sudden cardiac arrest (SCA) and death (SCD).

It is well established that the use of Implantable Cardioverter Defibrillators (ICDs) reduces the risk of mortality in patients with reduced left ventricular ejection fraction (LVEF) who are at risk of SCA or sustained ventricular tachycardia (VT). However, low ICD utilization in ICD-indicated patients worldwide (ranging from 30 to 50% in USA, 24% in Europe, 12% in Asia) and persistent high post-PCI mortality rates suggest that barriers in this patient care pathway exist.

Known barriers to ICD utilization include reimbursement (by government or insurance) of devices, lack of evidence awareness by healthcare providers, and limited ability and willingness to pay due to patients' socioeconomic status and attitudes. Greater uptake and patient acceptance generally occurs in regions with government reimbursement of ICDs and lower out-of-pocket patient cost; however, even in regions where this financial barrier is reduced, ICD referral rates remain low, suggesting challenges further upstream in the patient care pathway.

Efforts have been made to improve and align guidelines-based clinical practice for prevention of sudden death post-MI. For example, the ACC/AHA/HRS guidelines for post-MI care are widely accepted. In 2016, the Society of Cardiac Pacing and Electrophysiology, Chinese Society of Cardiology, Chinese Medical Association, and Heart Rhythm Committee of Chinese Medical Doctor Association jointly published an Expert Consensus Guideline for China, "Prevention of Sudden Cardiac Death after Revascularization to Coronary Heart Disease". These guidelines detail post-MI care and emphasize the importance of regular evaluation of the LVEF, but adherence has been low.

Ways in which the upstream care pathway can be improved have not been effectively implemented to date. A reduced LVEF more than 40 days after a MI identifies patients at higher risk of SCD.

Additionally, it is not known how many patients post MI have a LVEF that qualifies them for an ICD. This information is important because it provides visibility on areas to improve current revascularization approaches and sheds greater awareness on the magnitude of the ICD utilization problem in patients with reduced LVEF after MI.

The Improve SCA Bridge study will assess the care pathway for post-acute MI patients through standard assessment of LVEF and implementation of an educational strategy to bridge the treatment pathway for patients who are indicated for an ICD/CRT-D as per the AHA/ACC/HRS guideline.

The purpose of the Improve SCA Bridge study is to characterize the care pathway flow of post-acute MI patients as a result of standard assessments of left ventricular ejection fraction in acute phase (≤ 14 days post- acute MI) and chronic phase (≥ 40 -90 days post-acute MI). Specifically, how many patients are referred for sudden cardiac death (SCD) risk stratification and management, indicated for ICD/CRT-D implant, and how many receive such devices within 12 months of experiencing an MI. In addition, the current trial will characterize the impact from execution of the above-mentioned guidelines.

This Statistical Analysis Plan (SAP) will be used to support the final report and analysis of the Improve SCA Bridge study. The Statistical Analysis Plan has been designed to document, before data is analyzed, the planned analyses for the final report. This SAP does not limit the analysis in reports, and additional analyses of the study data beyond this plan might be conducted. However, this document provides the basis for the statistical sections of the final report. Analyses not planned in the SAP and incorporated into the final report will be referred to as "Additional Analysis". Further, in case any analyses will be

done differently than planned in the CIP or SAP and explanation will be provided in the final report. The following document was used to create this Statistical Analysis Plan (SAP): CIP Improve SCA Bridge Version 2, dated 1 MAY 2019.

4. Study Objectives

4.1 Primary Objective

To characterize the proportion of post-acute MI patients who are referred for sudden cardiac death (SCD) risk stratification and management.

4.2 Secondary Objectives

- Characterize the proportion of post-acute MI patients who are known to be indicated for an ICD/CRT-D* within 12 months post-acute MI.
- Characterize the proportion of post-acute MI patients who receive an ICD/CRT-D within 12 months post-acute MI.
- Summarize the referral and implant refusal rationale.
- Characterize the proportion of post-acute MI patients who experience cardiovascular mortality.
- Determine how the ejection fraction evolves over 3 months following an acute MI.

* Indication as per the current AHA/ACC/HRS Guideline for ICD (or CRT-D) implant

4.3 Endpoints

4.3.1 Primary Endpoint

The primary endpoint will be defined as the clinician's determination to refer the subject for an SCD stratification and management. The reason for this referral could be any of the following:

- Subject's LVEF at 3 months determined to be 40% or less
- Subject experiences unexplained syncope, ventricular arrhythmia, AV block, clinically significant palpitations, new onset bundle branch block, conduction abnormalities, or symptomatic bradycardia.

4.3.2 Secondary Endpoints

- For the objective "Characterize the proportion of post-acute MI patients who are known to be indicated for an ICD/CRT-D within 12 months post-acute MI" the endpoint will be defined as whether a subject was indicated for an ICD/CRT-D device during follow-up.

- For the objective “Characterize the proportion of post-acute MI patients who receive an ICD/CRT-D within 12 months post-acute MI” the endpoint will be defined as whether a subject received an ICD/CRT-D device during follow-up.
- For the objective “Summarize the referral and implant refusal rationale” the outcome measure will be the proportion of patients with ICD indication, who were not referred, refused referral or refused implant. The denominator will count all patients with at least one of the below:
 - (a) a reduced ejection fraction, as measured by the Left Ventricular Ejection Fraction (LVEF) being lower or equal than 40%.
 - (b) ventricular arrhythmia, AV block, new onset bundle branch block, or conduction abnormalities as measured by ECGs.
 - (c) unexplained syncope, clinically significant palpitations or symptomatic bradycardia as assessed by the physician.

The numerator will count the patients included in the denominator who were not referred, refused referral or refused implant of an ICD/CRT-D.

- For the objective “Characterize the proportion of post-acute MI patients who experience cardiovascular mortality” the endpoint will be defined as cardiovascular mortality.
- For the objective “Determine how the ejection fraction evolves over 3 months following an acute MI” the Left Ventricular Ejection Fraction (LVEF) will be measured acutely post MI (≤ 14 days after MI onset) and chronically (40-90 days). The endpoint will be the change between the acute and the chronic measurement.

5. Investigation Plan

5.1. Study Design

This study is a prospective, non-randomized, single-arm, multi-site, global, post-market study. There is no investigational device and there is no control group; subjects can be implanted, if indicated and referred, with any brand or model of a market released ICD/CRT-D.

The study is expected to be conducted at approximately 50 sites worldwide. Participating regions are: China, India, Korea, Middle East, Africa, Central Asia, & Turkey (MEACAT) (including Egypt, Pakistan, Saudi Arabia, South Africa and Tunisia), South East Asia (SEA) (including Brunei, Indonesia, Malaysia, Philippines, Singapore and Thailand) and Taiwan. Additional countries could participate within these regions. Each region is expected to enroll approximately 200 subjects. The study is expected to enroll approximately 1,200 subjects.

Prior to study site initiation, current referral information will be collected from sites, and investigators and other site clinical personnel will be trained using educational materials (available under a separate cover) that address the importance of EF measurement and care pathway for post-MI patients. Apart from the educational material, there is no intervention and there are no requirements for treatment of

the patients. Referral of patients to SCD risk stratification and management is at the discretion of the physicians.

[figure not shown]
Methods incorporated in the study design to minimize potential bias include (but are not limited to):

- Subject demographics will be collected at baseline for potentially analyzing differences that may affect the endpoints.
- All study clinicians and Medtronic personnel will be trained on the corresponding aspects of the study using standardized training materials.
- All study clinicians and Medtronic personnel will be trained on and required to follow the Protocol.
- Sites will be encouraged to approach any eligible patients meeting inclusion/exclusion criteria
- Each region is expected to enroll approximately 200 subjects to have at least 80% power to achieve a sufficient number of patients referred for SCD risk stratification and management.
- For each region, sites where the same physician acts both as an interventional cardiologist and as an electrophysiologist will be limited to a maximum of 20% of all sites.

No interim analysis is planned, but a sample size re-assessment for each region may be produced, as described in Section 6.2.

See Figure 1 for further detail on study procedures.

Figure 1 Study Flow

***For patient enrollment:** Patients must be enrolled ≤ 30 days post-acute MI and must have an $EF < 50\%$ measured ≤ 14 days post-acute MI.

****Referral Criteria:** sustained VT, cardiac or unexplained syncope, clinically significant palpitations, new onset bundle branch block, conduction abnormalities, or symptomatic bradycardia.

Table 1 below specifies the time windows for the required subject visits, which are based on days post-acute MI. If a subject visit falls outside the pre-specified window, a study deviation will be reported, and the original follow-up schedule maintained for subsequent visits.

Data analyses will include follow-up visits, regardless of whether the visits occur within the time window. If a subject has an out of window visit, referral will be counted at the consecutive visit, while non-referral will be counted at the previous visit. For example, if a subject has a 3 months visit at 140 days post MI and is referred, he'll be considered as having been referred at the 6 months visit. On the contrary, if a subject has a 3 months visit at 140 days post MI and is not referred, he'll be considered as not having been referred at the 3 months visit. Rationale of this is:

1. When the late visit does not have the event (e.g. no referral yet), the event also had not happened yet in the window of the previous visit, but it may occur at the consecutive visit.
2. When the late visit has the event (e.g. referral), the status at the next visit is referred, but it is unsure whether the referral would have already happened in the window of the previous visit.

Table 1: Follow-up windows

Study Follow-up Visit	Window (Calculated days post-acute MI)		
	Window Start (days post-MI)	Target (days post-MI)	Window End (days post-MI)
3 month	40	90	120
6 month	150	180	210
12 month	335	365	395

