9.3. Schedule of Events

Clinical data will be collected at the Baseline 3 month, 6 month, 12 month, and exit visits. In addition if applicable, clinical data will be collected with an exit or death, as well as unscheduled visits. Device data will be collected from device interrogations on Medtronic devices received during the period between the enrollment and exit until study closure; for non-Medtronic devices, device data will not be collected. Data will be collected using eCRFs using an electronic data management system for clinical studies. In addition to eCRF data, non-eCRF data will be collected including device interrogation files (for Medtronic implanted devices only). Surveys may also be used throughout the study.

Data will be stored in a secure, password-protected database, which will be backed up nightly. Data will be reviewed using programmed and manual data checks. Data queries will be made available to study sites for resolution. Study management reports will be generated by Medtronic to monitor data quality and study progress. At the end of the study, the data will be frozen and retained indefinitely by Medtronic. Data Collection requirements are summarized in the table 2 below.

Table 2 Data Collection and study procedure requirements at subject visit

Study Procedure	Baseline	3 month visit	6 month visit	12 month visit	Study Exit
Patient informed consent	X				
Eligibility Verification (Inclusion/ exclusion assessment)	X				
Subject Demographics	X				
Acute MI information	X				
Medical History	X				
Cardiovascular Medications	X	X			
LVEF measurement	X	X*	X (collect if performed as per SOC)	X (collect if performed as per SOC)	
ECG	X	X (collect if performed as per SOC)	X (collect if performed as per SOC)	X (collect if performed as per SOC)	
Referral Status		X	X	X	X
Implant Status (if applicable)		X (if subject receives or has received device implant)	X (if subject receives or has received device implant)	X (if subject receives or has received device implant)	X (if subject receives or has received device implant)
Device Interrogation File (pdd) or CareLink Transmission for subjects implanted with Medtronic device only		X	X	X	X
Adverse Event	As they occur				
System Modification					
Study Deviation					
Subject Death					

* The LVEF measurement needs to be performed ≥ 40 days post-acute MI for MI subjects without revascularization, or ≥ 90 days post-revascularization for post-MI subjects with revascularization done.

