6.1 Sample Size Assessment

The sample size calculation was based on the width of the 95% confidence interval for the proportion of subjects that is referred for SCD risk stratification and management among subjects who have a reason for referral at the 3 months visit. The following assumptions were made:

- Drop-out and mortality rate combined from enrollment to 3 months visit of 10%,
- At the 3 months visit, 30% of subjects will have a reason for referral.

Under these assumptions, enrollment of approximately 200 patients per region is needed, to have at least 80% power to achieve a 95% confidence interval width of 25% when 70% of patients with a reason for referral at the 3 months visit is referred for SCD risk stratification and management.

The sample size has been computed as follows.

First, the number of subjects needed in each region with a reason for referral at the 3 months visit ($N_{\text{reason_referral}}$) was computed using the SAS procedure below:

```
proc power;
onesamplefreq
  ci = wilson
  halfwidth = 0.125
  probwidth = .
  proportion = 0.70
  ntotal = 40 to 70 by 1;
run;
```

where proportion = 0.70 is the proportion of subjects to be referred among those with a reason for referral and halfwidth = 0.125 is half of the 95% confidence interval around this proportion. As a result of the above SAS procedure, the needed number of subjects that will give at least 80% power to achieve a 95% confidence interval of halfwidth = 0.125 around a proportion of 70% of subjects with a reason for referral that will be referred is $N_{\text{reason_referral}} = 54$.

Secondly, the number of subjects expected at the 3 months visit was computed as the ratio between the required number of subjects with a reason for referral at the three months visit ($N_{\text{reason_referral}} = 54$) and the assumed proportion of subjects with a reason for referral at the three months visit ($\text{prop}_{\text{referral_assumed}} = 0.30$) :

$$N_{\text{3months}} = \frac{N_{\text{reason_referral}}}{\text{prop}_{\text{referral_assumed}}} = \frac{54}{0.30} = 180$$

The number of subjects to be enrolled was then computed as the expected number of subjects that will complete the three months visit ($N_{\text{3months}} = 180$) and the assumed proportion of subjects that will not drop-out or die between enrollment and the 3 months visit ($1 - \text{rate}_{\text{exit_assumed}} = 0.90$):

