7.2 General Methodology

Data summaries for categorical data will include count, e.g., number of patients, and/or number of events, and a percentage relative to the total number of patients/events. The denominator will be explicitly identified when not clear from the context. Continuous variables will be represented by mean and standard deviation, except when the distribution of the variable is highly skewed in which case median and quartiles will be reported.

P-values for hypothesis testing will be evaluated based on two-sided testing using significance level of 0.05. Confidence intervals will be reported as two-sided 95% confidence intervals.

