Table 2: Number (%) of subject in each group between enrollment and the 3 months visit

		Enrolled Population
Region 1	Died of cardiovascular causes	XX/XX (XX.XX%)
	Exited or died of non-cardiovascular or unknown causes	XX/XX (XX.XX%)
	Reached the 3 months visit and exited because of LVEF \geq 50%	XX/XX (XX.XX%)
	Reached the 3 months visit and had reasons for referral	XX/XX (XX.XX%)
	Reached the 3 months visit and had no reasons for referral	XX/XX (XX.XX%)
Region 2	Died of cardiovascular causes	XX/XX (XX.XX%)
	Exited or died of non-cardiovascular or unknown causes	XX/XX (XX.XX%)
	Reached the 3 months visit and exited because of LVEF \geq 50%	XX/XX (XX.XX%)
	Reached the 3 months visit and had reasons for referral	XX/XX (XX.XX%)
	Reached the 3 months visit and had no reasons for referral	XX/XX (XX.XX%)
...
Overall	Died of cardiovascular causes	XX/XX (XX.XX%)
	Exited or died of non-cardiovascular or unknown causes	XX/XX (XX.XX%)
	Reached the 3 months visit and exited because of LVEF \geq 50%	XX/XX (XX.XX%)
	Reached the 3 months visit and had reasons for referral	XX/XX (XX.XX%)
	Reached the 3 months visit and had no reasons for referral	XX/XX (XX.XX%)

The same summary statistics will be computed at the 6 months and at the 12 months visits and displayed in tables similar to Table 1, except for the group “exited because of LVEF \geq 50%” as patients are exited from the study for this reason at the 3 months visit only.

Note that at the three months visit, subjects with a LVEF \geq 50% will be exited from the study regardless of other reasons for referral. The proportion of those subjects that had a reason for referral other than LVEF will be computed by region and overall.

Among the subjects with a reason for referral during their three months visit, the proportions and Wilson score 95% CI of those who were referred for sudden cardiac death risk (SCD) stratification and management will be computed.

The subjects with a reason for referral (denominator) will be all subjects that at the three months visit will have at least one referral criterion met in the referral CRF. The subjects referred (numerator) will be

all subjects that will have completed the three months visit and that will have answer “yes” to the question “has the subject been referred or invited for SCD risk stratification” in the referral CRF.

An example SAS code for the computation of the proportions for each region is provided below:

```
proc freq data = referral;
  by region;

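### SAP 5.1 assigns a late 3-month visit to a time point by its outcome, which conflicts with the primary definition in SAP 7.9.1.3 and lowers the 3-month referral proportion

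*SAP*

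**What the plan says.** SAP 5.1 (Table 1) sets the 3-month window at day 40 to day 120 after MI, with target day 90. Out-of-window visits stay in the analysis, but "referral will be counted at the consecutive visit, while non-referral will be counted at the previous visit". In its example, a subject referred at a 3-month visit on day 140 is "considered as having been referred at the 6 months visit", while a subject not referred on that day counts as not referred at 3 months. The reason given is that a late non-referral implies no referral inside the window, whereas for a late referral "it is unsure whether the referral would have already happened in the window of the previous visit".

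SAP 7.9.1.3 defines the primary proportion without mentioning this rule. The denominator is "all subjects that at the three months visit will have at least one referral criterion met in the referral CRF". The numerator is "all subjects that will have completed the three months visit and that will have answer" yes to the referral question on that form. Neither definition has a date limit. Protocol 9.6 also keeps out-of-window visits in the analysis and has no reassignment rule.

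**The concern.** Take a subject seen for the 3-month visit on day 140 who meets a referral criterion and is referred. Under SAP 7.9.1.3 this is a 3-month success. Under SAP 5.1 it is not. Two programmers could follow the SAP and report different primary results from the same data.

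The 5.1 rule also leaves the denominator open. The subject met a criterion at the 3-month visit, so Table 2 of the SAP counts them as having reached that visit with a reason for referral. Whether they remain in the Table 3 denominator is not stated.

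If 5.1 governs, the primary estimate depends on visit punctuality as well as referral practice, because late successes move and late failures do not. Results are reported by region, centres are compared by Fisher's exact test (SAP 7.3), and PCI status is a named factor in the logistic models. Groups with different late-visit shares would be affected differently.

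The rule has two further gaps. It refers to out-of-window visits in general, but the rationale covers only late ones, so visits before day 40 are unexplained. It also cannot be applied to a referral at a 12-month visit after day 395, because Table 1 has no later visit.

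**Working it through.** **Planned precision.** SAP 6.1 uses a Wilson interval and a referral proportion of 0.70, and "halfwidth = 0.125 is half of the 95% confidence interval around this proportion". The interval is two-sided 95% (SAP 7.2). The exact binomial probability that the half-width is at most 0.125 is 0.784 at n = 53 and 0.897 at n = 54. The smallest n reaching 80% is therefore 54. Then 54/0.30 = 180 and 180/0.90 = 200. The plan's figures reproduce.

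**Direction.** Among subjects with a reason for referral, let R1 and N1 be the on-time referred and not referred, and R2 and N2 the late referred and not referred.

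- SAP 7.9.1.3: (R1+R2)/(R1+R2+N1+N2)
- Excluding all late visits: R1/(R1+N1)
- SAP 5.1, reading A (late-referred leave the denominator): R1/(R1+N1+N2)
- SAP 5.1, reading B (late-referred stay as not referred): R1/(R1+R2+N1+N2)

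A takes only successes away from the 7.9.1.3 count, and adds only failures to the on-time count. B is never above A. Both readings are therefore at or below both comparators.

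**Size.** The late share q is not in the documents, so 5% to 30% is an assumed range. Referral is taken as p = 0.70 (SAP 6.1) for late and on-time visits alike. Then 7.9.1.3 gives p, A gives p(1−q)/(1−pq), and B gives p(1−q). The denominator under A is 54(1−pq).

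| q | 7.9.1.3 | A (shift, points) | B (shift, points) | Denominator under A |
|---|---|---|---|---|
| 5% | 70.0% | 68.9% (−1.1) | 66.5% (−3.5) | 52.1 |
| 10% | 70.0% | 67.7% (−2.3) | 63.0% (−7.0) | 50.2 |
| 20% | 70.0% | 65.1% (−4.9) | 56.0% (−14.0) | 46.4 |
| 30% | 70.0% | 62.0% (−8.0) | 49.0% (−21.0) | 42.7 |

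The shift under B passes 12.5 points at q = 0.125/0.70 = 17.9%. Under A it does so only at about 42%: 0.70 × 0.58/(1 − 0.294) = 0.575.

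**Precision under A.** At q = 10% about 50 subjects remain. At p = 0.70 the probability of meeting the planned width falls from 0.90 to 0.57, below the 80% target.

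**Example in counts.** Suppose 54 subjects have a reason for referral, 38 are referred, and 4 of those are late.

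- 7.9.1.3: 38/54 = 70.4% (Wilson 95% CI 57.2% to 80.9%)
- A: 34/50 = 68.0% (54.2% to 79.2%)
- B: 34/54 = 63.0% (49.6% to 74.6%)

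**Between regions.** Two regions that both refer 70%, with 5% and 20% late visits, would appear to differ by 68.9 − 65.1 = 3.8 points (A) or 66.5 − 56.0 = 10.5 points (B).

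**Against status by day 120.** If none of the late referrals would have occurred in window, the true figure is p(1−q). B is then exact, and A is too high by 2.4, 4.7, 9.1 and 13.0 points at the four values of q. The direction against this target depends on the denominator that the SAP leaves unstated.

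**Why lateness may differ by PCI status.** Protocol 9.3 requires the 3-month LVEF at least "90 days post-revascularization for post-MI subjects with revascularization done". For revascularisation on day d, the in-window time left is 120 − (90 + d) = 30 − d days, against 120 − 40 = 80 days without revascularisation. A late LVEF is forced only when d exceeds 30.

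**The case against.** SAP 5.1 is the only passage that deals with out-of-window visits in detail, and a specific rule is often read as governing a general definition that is silent. SAP 7.9.1.3 opens by labelling the visit as chronic phase, days 40 to 90, and SAP 7.9.2.3 refers to the 3-month visit window in an example, so a time-bound reading has support. SAP 7.9.1.4 takes, at each visit, the subjects with a reason for referral at that visit, which may favour reading A and its smaller shifts. The sponsor gave a reason for the rule. Counting a day-140 referral at 3 months also gives late attenders more time to be referred. The competing-risk curves in SAP 7.9.3.3 use referral dates, and the study is descriptive with no planned test between regions.

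Part of this stands. The size is assumed, and under A with few late visits it is small. The differential lateness by region or PCI status is hypothetical, and the LVEF timing rule does not bind the other referral criteria. The preferred target is a design choice.

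It does not remove the problem. The chronic-phase label is narrower than the day-120 window and does not say that 5.1 prevails. SAP 7.9.1.4 does not settle the denominator for a subject who met a criterion at a late 3-month visit. The stated reason concerns status by day 120. It does not justify keeping late failures while removing late successes (A), and B treats every uncertain referral as a failure. The competing-risk curves are not restricted to subjects with a reason for referral, so they do not replace the primary proportion.

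**Conclusion.** The concern holds. The two SAP sections classify the same late-referred subject differently, and nothing in the documents resolves it. Under either denominator, SAP 5.1 lowers the 3-month proportion relative to SAP 7.9.1.3 as soon as one late visit ends in referral (reading A also needs at least one subject not referred). This is a fault in the rule as written and goes beyond missing detail.

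The direction is certain for late visits against that comparator. The size rests on an assumed late share and equal referral in late and on-time visits. At 10% late it is 2.3 or 7.0 points, depending on the denominator. The sample size of 200 per region is not itself in error. The point should be fixed before analysis.

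**What to change.** Replace the rule in SAP 5.1 so that each nominal 3-month visit counts at 3 months whatever its date and outcome, as SAP 7.9.1.3 is written. State that late-referred subjects are in both the numerator and the denominator. Apply the same symmetric rule at 6 and 12 months, which also removes the problem after day 395, and say how visits before the window opens are handled.

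Add one sensitivity analysis that excludes all late visits regardless of outcome, and report the late-visit share by region. An analysis by actual referral date, on or before day 120, may be added if it is labelled as status by day 120 and as a lower bound for what on-time visits would have shown.

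The cost is one SAP paragraph, one derivation change and one extra table. No new data are needed, because visit dates are already required to identify out-of-window visits and referral dates are already needed for the curves in SAP 7.9.3.3.
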